10. Subject has donated blood or blood products (e.g., plasma or platelets) within the 3 months prior to screening.
11. Subject has a partner who will be pregnant or breastfeeding during the study

12. Pregnant or breastfeeding female or those with a positive pregnancy test or who will not use a medically acceptable contraceptive method from selection and during the study
13. Subject having used corticosteroid sporadically in the last 30 days whichever the route of administration, or any medication by ocular or nasal administration route
14. Subjects diagnosed with any ocular disease other than refractive error
15. Subject with history of ocular surgery, including laser refractive surgery
16. Subject using a contact lens within 7 days prior administration of the first dose
17. Intraocular pressure (IOP) ≥ 22 mmHg in either eye at screening or baseline
18. Presence of any corneal opacity or corneal fluorescein staining >0.5 grade using the modified Oxford scale in either eye at screening or baseline
19. Schirmer's test without anesthesia ≤ 9 mm/5 minutes in either eye at screening or baseline
20. Tear film break up time (TFBUT) < 8 seconds in either eye at screening or baseline

Note: Alcoholic beverages should not be taken from 48 h before first drug administration until discharge from the Study center. There are also restrictions with regard to chewing gum, heavy exercise and smoking (See § 7.6).

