The examiner should not stand close to the chart during testing. Attention should be focused on the subject and the VA worksheet. If the subject has difficulty locating the next line to read, the examiner may go up to the chart and point briefly to the next line to be read, but then must move away from the chart.

When 20 or more letters are read at 4 meters the visual acuity score for that eye is recorded as the number of letters correct at 4 meters plus 30 (refer to the VA worksheet). The subject gets credit for the 30 letters at 1 meter even though they did not have to read them. Otherwise, the visual acuity score is the number of letters read correctly at 1 meter plus the number, if any, read at 4 meters. If no letters are read correctly at either 4.0 meters or 1 meter, then the visual acuity score is recorded as “0.”

Clinically significant changes (or a clinically significant worsening) in BCDVA, which were observed the first time during study will be reported as adverse event.

External ocular examination (EOE): motility and eyelids

External Ocular Examination assesses the motility of the extraocular muscles and the appearance and function of the eyelids before the instillation of any dilating or anesthetic eye drops.

Clinically significant changes (or a clinically significant worsening) in EOE, which were observed the first time during study will be reported as adverse event.

Slit-lamp examination (SLE)

SLE to assess the eyelid margin, conjunctiva, cornea, anterior chamber, iris and lens. The Slit-lamp examination (SLE) must be performed before the instillation of any dilating or anesthetic eye drops or the fluorescein agent. The subject will be seated at the slit-lamp while being examined. Grading of the eyelids, lashes, conjunctiva, cornea, lens, iris and anterior chamber will be done according to the following scales:

Eyelid - Meibomian glands

Evaluation of the central ten Meibomian gland openings in the mid-portion of the upper eyelid:

- 0 = None (none are plugged).
- 1 = Mild (1 to 2 glands are plugged).
- 2 = Moderate (3 to 4 glands are plugged).
- 3 = Severe (All glands are plugged).

Eyelid - Erythema

- 0 = None (normal).
- 1 = Mild (redness localized to a small region of the lid(s) margin OR skin).
- 2 = Moderate (redness of most or all lid margin OR skin).
- 3 = Severe (redness of most or all lid margin AND skin).
- 4 = Very severe (marked diffuse redness of both lid margin AND skin).

Eyelid - Edema

- 0 = None (normal).

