- 1 = Mild (localized to a small region of the lid).
- 2 = Moderate (diffuse, most or all lid but not prominent/protruding).
- 3 = Severe (diffuse, most or all lid AND prominent/protruding).
- 4 = Very severe (diffuse AND prominent/protruding AND reversion of the lid).

Lashes

- 0 = Normal.
- 1 = Abnormal (specify).

Conjunctiva – Erythema

- 0 = None (normal).
- 1 = Mild (a flush reddish color predominantly confined to the palpebral or bulbar conjunctiva).

2 = Moderate (more prominent red color of the palpebral or bulbar conjunctiva). 3 = Severe (definite redness of palpebral or bulbar conjunctiva).

Conjunctiva - Edema

0 = None (normal).

1 = Mild (slight localized swelling).

2 = Moderate (moderate/medium localized swelling or mild diffuse swelling).

3 = Severe (severe diffuse swelling).

4 = Very severe (very prominent/protruding diffuse swelling).

Lens

0 = No opacification (normal lens).

1 = Mild lens opacification.

2 = Moderate lens opacification.

3 = Severe lens opacification.

N/A = Subject with artificial lens

Iris

0 = Normal

1 = Abnormal.

Anterior Chamber Inflammation (Slit beam = 0.3 mm wide, 1.0 mm long)

0 = None (no Tyndall effect).

1 = Mild (Tyndall effect barely discernible).

2 = Moderate (Tyndall beam in the anterior chamber is moderately intense).

3 = Severe (Tyndall beam in the anterior chamber is severely intense).

Corneal findings of interest on the SLE include also the horizontal diameter of the cornea (measured in mm at the time of the SLE using a ruler).

Clinically significant changes (or a clinically significant worsening) in SLE, which were observed the first time during study will be reported as adverse event.

Corneal fluorescein staining (modified Oxford scale)

As grading scale of the corneal and conjunctiva damage, the NEI/Industry Workshop guidelines will be used [Reference: 2]. The cornea is divided into five sectors (central, superior, inferior, nasal and temporal), each of which is scored on a scale of 0–3, with a maximal score of 15. Both nasally and temporally, the conjunctiva is divided into a superior paralimbal area, an inferior paralimbal area and a peripheral area with a grading scale of 0–3 and with a maximal score of 9 for the nasal and temporal conjunctiva.

For a better reading it is also essential not to use an intense illumination beam, which may reduce the contrast and lead to an underestimation of grading [Reference: 3].

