Anterior Chamber Inflammation	0 = None (no Tyndall Effect) 1 = Mild (Tyndall Effect barely discernable) 2 = Moderate (Tyndall beam in the anterior chamber is moderately intense) 3 = Severe (Tyndall beam in the anterior chamber is severely intense)
Other	Specification and assessment of other investigated eye structure

For each eye structure, the investigator will have the opportunity to tick also ‘Not done/Not evaluable’, which will be treated as ‘Missing’ for analysis purposes.

Clinically significant changes (or a clinically significant worsening) in SLE, which were observed the first time during study will be reported as adverse event.

All grading assessments of different eye structures will be evaluated as collected on the eCRF. No imputation will be envisaged for these parameters.

No aggregated presentation is planned for other assessments done during Slit lamp evaluation.

Fundus Ophthalmoscopy

Fundus ophthalmoscopy to assess the eye structure will be performed and results recorded on the eCRF page “Fundus Ophthalmoscopy” by utilizing the following assessments.

Eye Structure	Rating
Vitreous	0 = Normal 1 = Abnormal (specify) 2 = Not done/Non-Evaluabe
Retina / Macula	0 = Normal 1 = Abnormal (specify) 2 = Not done/Non-Evaluabe
Choroid	0 = Normal 1 = Abnormal (specify) 2 = Not done/Non-Evaluabe
Optic Nerve	0 = Normal 1 = Abnormal (specify) 2 = Not done/Non-Evaluabe
Cup/Disc Ratio	0 = Normal 1 = Abnormal (specify) 2 = Not done/Non-Evaluabe In addition, the Cup/Disc Ratio is recorded

Dilated FO will be performed at Screening Visit with non-dilated FO performed at Baseline Visit 0 hr, FU2 8hr and FU3 0hr. Clinically significant changes (or a clinically significant worsening) in FO, which were observed the first time during study will be reported as adverse event.

Physical Examination

Physical Examination includes an examination of general appearance, head-eyes-throat-nose-ears (HEENT), skin, thorax/lungs, cardiovascular system, abdomen, lymph nodes, musculoskeletal system, neurological system and other examinations as necessary.

The clinical evaluation ('Normal', 'Abnormal, Not Clinically Significant', 'Abnormal, clinically significant'). It is collected on eCRF Page "Physical Examination" at Screening Visit, Baseline Visit, FU1, FU2 and FU3.

Clinically significant abnormalities (or a clinically significant worsening of a physical condition), which were observed the first time during study will be reported as adverse event.

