10.8 Other Safety Variables

External Ocular Examination (EOE)

All evaluations of the motility of extraocular muscle Right and Up, Right, Right and Down, Left and Up, Left, Left and Down will be summarized descriptively by treatment group and study visit for the Study Eye as well as the Non-Study Eye. This analysis will be performed on the SAF. These data will also be listed for the SAF.

Incidences of proven eyelid deformity/abnormality, abnormal motor function of eyelids, corneal exposure in case of closed eyelid, proven punctal occlusion, punctal plugs, thermal or surgical occlusion or other punctal occlusion will be presented for the SAF by treatment group and study visit for the Study Eye as well as for the Non-Study.

Moreover, these data will be listed for the SAF.

Slit Lamp Evaluation

All grading assessments of different eye structure (excluding assessment for other structures) will be summarized descriptively for the SAF by treatment group and study visit for the Study Eye as well as the Non-Study Eye.

All data recorded on the eCRF page 'Slit Lamp Examination (Biomicroscopy)' will be listed for the SAF.

Fundus Ophthalmology

All data including details on detected abnormalities recorded on the eCRF will be listed for the SAF clearly indicating the mode of assessment (Dilated/Not-Dilated).

Physical Examination

All physical examination data recorded on the eCRF will be listed for the SAF.

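### The protocol promises slit-lamp grading of the cornea but gives no corneal item, so non-staining corneal findings short of an adverse event are listed but not tabulated; separately, the Meibomian grades skip 5 to 9 of ten glands

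*Protocol*

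**What the plan says.** Protocol 8.12, under slit-lamp examination, names seven structures to be graded: "Grading of the eyelids, lashes, conjunctiva, cornea, lens, iris and anterior chamber will be done according to the following scales". The scales that follow cover Meibomian glands, lid erythema, lid oedema, lashes, conjunctival erythema, conjunctival oedema, lens, iris and anterior chamber inflammation. The cornea then appears once more in that subsection: "Corneal findings of interest on the SLE include also the horizontal diameter of the cornea". That is a measurement in millimetres, not a grade, and SAP 3.6 reports that it was not collected.

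SAP 7.2.16 repeats the nine scales and adds an 'Other' row for any other structure. It then says: "No aggregated presentation is planned for other assessments done during Slit lamp evaluation". SAP 10.8 agrees: "All grading assessments of different eye structure (excluding assessment for other structures) will be summarized descriptively". All data on the slit-lamp eCRF page are listed for the Safety Set.

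For the Meibomian item the protocol specifies "Evaluation of the central ten Meibomian gland openings in the mid-portion of the upper eyelid". Grade 0 is no plugged glands and grade 1 is one or two. The remaining grades are "2 = Moderate (3 to 4 glands are plugged)" and "3 = Severe (All glands are plugged)". The SAP carries the same grades.

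**The concern.** This is an eye-drop safety study, and the slit lamp is one of the examinations in which a corneal change would be seen. The cornea matters for entry too: exclusion criterion 18 bars "Presence of any corneal opacity or corneal fluorescein staining >0.5 grade using the modified Oxford scale". Yet lashes and iris each have a normal/abnormal row, and the cornea has none.

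A finding such as faint opacity or mild oedema, if not judged clinically significant, has only the free-text row to go to. That row is not tabulated. It also gives no usable denominator, because an empty 'Other' field does not separate a normal cornea from one on which nothing was recorded. The slit-lamp table therefore cannot show how many study eyes kept a normal cornea on rhNGF compared with vehicle.

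The Meibomian gap is a different matter, at the lid margin. An examiner who counts five to nine plugged openings has no valid grade. The choice is a wrong grade or the tick for not done or not evaluable, which SAP 7.2.16 treats as missing.

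**Working it through.** There is no sample-size, power or event figure to reproduce. The check is a count and a comparison of passages.

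**1. Structures named against scales supplied** (Protocol 8.12; SAP 7.2.16)

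| Structure named for grading | Scales supplied |
|---|---|
| Eyelids | 3 (Meibomian glands, erythema, oedema) |
| Lashes | 1 |
| Conjunctiva | 2 (erythema, oedema) |
| Cornea | 0 |
| Lens | 1 |
| Iris | 1 |
| Anterior chamber | 1 |

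Total: 3 + 1 + 2 + 0 + 1 + 1 + 1 = 9 scales. Six of the seven named structures have at least one; the cornea has none, in either document.

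**2. Time points affected.** SAP 7.2.16 schedules slit lamp at Screening, Baseline, D1 8 h, D2 pre-dose, D2 8 h, D3 pre-dose, D6 pre-dose, D6 8 h, FU1, FU2 and FU3. That is 11 per eye.

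**3. Where a corneal finding can go**

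- It shows as fluorescein staining: scored in five sectors at 0 to 3 each, 5 × 3 = 15 maximum (SAP 7.2.15), and summarised by eye, arm and visit with change from baseline (SAP 10.7.7; Tables 14.4-9.1 and 14.4-9.2).
- It is a clinically significant change at slit lamp: reported as an adverse event (Protocol 8.12) and counted in the TEAE tables, which include ocular TEAEs by eye (SAP 10.6.1).
- It is neither: it goes in the 'Other' row, is listed, and enters no table (SAP 7.2.16 and 10.8).

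Only the third route is deficient. The staining score does not obviously absorb it. Protocol 8.12 places the slit-lamp examination before fluorescein is instilled, and the staining score consists of sector grades with no separate item for opacity or oedema.

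**4. Disclosure.** SAP 3.6 reports the uncollected corneal diameter but does not mention the missing corneal grade.

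**5. Meibomian counts.** Ten openings give 11 possible counts, 0 to 10.

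- Covered: 0 (grade 0); 1, 2 (grade 1); 3, 4 (grade 2); 10 (grade 3). That is 1 + 2 + 2 + 1 = 6.
- Not covered: 5, 6, 7, 8, 9. That is 11 − 6 = 5.

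Five of 11 describes the scale. It is not an estimate of how often data would be lost.

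**The case against.** A reader might infer that slit-lamp findings in the directly dosed tissue are never graded or tabulated. The documents do not support that:

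- The conjunctiva is also directly dosed. Its erythema (0 to 3) and oedema (0 to 4) are graded and go into Table 14.5-3.1.
- The cornea is scored by NEI staining at the same 11 time points and tabulated with change from baseline. The overall NEI score is a named secondary safety endpoint.
- Both documents' schedule notes treat slit lamp and fluorescein staining as one block, and the protocol describes the NEI scale as grading corneal and conjunctival damage. The grading sentence may simply lack a cross-reference to it.
- Clinically significant slit-lamp changes become adverse events, and TEAE incidence is a primary endpoint.
- With 30 subjects and no inferential analysis, a by-subject listing can be read in full.

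All of this stands and limits the point to non-staining corneal findings below the adverse-event threshold. It does not remove the point, because a listing of free-text entries gives no comparison by arm, eye and visit.

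Two further inferences fail. Exclusion 18 is not unworkable: absence of opacity is a yes/no check that needs no severity scale, and inclusion criterion 5 already requires a normal anterior segment at Screening and Baseline. Nor does the Meibomian gap bear on corneal grading. It may seldom matter, since entrants must have a normal anterior segment and no ocular disease other than refractive error, and they are dosed for six days. The scale is still not exhaustive.

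**Conclusion.** The point holds in a limited form, at low severity. One of the seven structures that the protocol says will be graded at slit lamp has no scale in the protocol or the SAP. The consequence is confined to corneal findings that the staining score does not capture and that are not reported as adverse events. These reach the study report only as free-text listing entries. Separately, 5 of 11 possible Meibomian counts have no grade and would be misgraded or treated as missing.

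No primary endpoint (TEAE incidence, change in VAS tolerability) and no stated figure is affected. The conclusion assumes that the eCRF slit-lamp page matches the SAP 7.2.16 table, which the SAP presents as the assessments recorded there. How often either gap would arise cannot be derived from the documents.

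**What to change.** **Cornea.** Add a row 'Cornea: 0 = normal, 1 = abnormal (specify)' to the slit-lamp scales in Protocol 8.12, to the eCRF page and to the SAP 7.2.16 table, and summarise it by eye, arm and visit in Table 14.5-3.1. The SAP describes much of the eCRF collection in the past tense, so the eCRF change may come too late. In that case, code corneal entries from the 'Other' row while the study is still masked, most naturally at the blind data review meeting, and tabulate those. Late coding recovers recorded abnormalities but cannot confirm normal corneas where the field was left empty; the table should carry a note saying so. Merely replacing the cornea in the grading sentence with a reference to the staining score would remove the inconsistency but leave the gap.

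**Meibomian glands.** Make the grades exhaustive, for example by letting the top grade cover every count above 4. The documents give no basis for any particular cut, so this is an illustration. If data are already collected, leave the grades as recorded and state how counts of 5 to 9 were graded.

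**Disclosure.** Record both changes in SAP 3.6.

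**Cost.** One extra table row and one change of scale wording, or a short masked coding exercise if collection is complete. The cornea is already examined at every slit-lamp visit, so no new procedure is needed.

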9 EVALUATION OF ADVERSE EVENTS AND SAFETY INFORMATION

AE definition, classification and management will follow the Sponsor SOPs, based upon applicable local and international regulations. A brief summary of AE definition, classification and management is reported below.

9.1 Definitions

Adverse Event

An **Adverse Event (AE)** is defined as any untoward medical occurrence in a subject or clinical investigation subject administered a medicinal product and which does not necessarily have a causal relationship with this treatment (CFR-Code of Federal Regulations Title 21 Sec. 312.32). An AE can therefore be any unfavourable and unintended sign (including an abnormal laboratory finding), symptom, or disease temporally associated with the use of a medicinal (investigational) product, whether or not related to the medicinal (investigational) product.

Non-Serious Adverse Event (NSAE)

A **non-serious AE (NSAE)** is defined as any untoward change in a subject's medical conditions that does not meet serious criteria noted below (e.g., is not fatal, is not life-threatening, does not require hospitalization, does not prolong a current hospitalization, is not disabling and is not an important medical event).

Serious Adverse Event (SAE)

A **Serious Adverse Event (SAE)** is defined in line with CFR-Code of Federal Regulations Title 21 Sec. 312.32 as any adverse experience that meets any of the following criteria:

- results in death;
- is life-threatening;

NOTE: Life-threatening means that the subject was at immediate risk of death from the reaction as it occurred, i.e., it does not include a reaction which hypothetically might have caused death had it occurred in a more severe

- requires inpatient hospitalization or prolongation of existing hospitalization;

NOTE: In general, hospitalization means that the individual remained at the hospital or emergency ward for observation and/or treatment (usually involving an overnight stay) that would not have been appropriate in the physician's office or an outpatient setting. Complications that occur during hospitalization are AEs. If a complication prolongs hospitalization or fulfills any other serious criteria, the event is serious. When in doubt as to whether "hospitalization" occurred, the event should be considered serious.

- results in persistent or significant disability/incapacity;

NOTE: The term disability means a substantial disruption of a person's ability to conduct normal life functions. This definition is not intended to include experiences of relatively minor medical significance such as uncomplicated headache, nausea, vomiting, diarrhea, influenza, or accidental trauma (e.g., sprained ankle) which may interfere or prevent everyday life functions but do not constitute a substantial disruption).

- results in a congenital anomaly/birth defect;
- is an important medical event

NOTE: An important medical event is an event that may not result in death, be life-threatening, or require hospitalization but may be considered a SAE when, based upon appropriate medical judgment, it may jeopardize the subject's well being and may require medical or surgical intervention to prevent one of the outcomes listed in the definitions for SAEs. Examples of such medical events include allergic bronchospasm requiring intensive treatment in an emergency room or at home, blood dyscrasias or

convulsions that do not result in subject hospitalization or the development of drug dependency or drug abuse.

Death shall always be reported as SAE: a death due to progression of disease would not have a causal relationship to the product. The investigator should report the event immediately to the sponsor, but the sponsor will not report the event as expedited to the regulatory authority. Cause of death shall always be specified when known or duly investigated.

Sight Threatening Event

For this study medically important events comprise the following sight threatening events, which are considered to be of special interest and by default are to be reported as SAEs:

- Adverse Events that caused a decrease in visual acuity of >30 ETDRS letters or > +0.6 LogMAR (compared with the last assessment of visual acuity at the last visit) lasting >1 hour
- Adverse Events that cause a decrease in visual acuity to the level of Light Perception or worse lasting >1 hour
- Adverse Events that require surgical intervention (e.g., conventional surgery, vitreous tap or biopsy with intravitreal injection of anti-infectives, or laser or retinal cryopexy with gas) to prevent permanent loss of sight
- Adverse Events associated with severe intraocular inflammation (i.e., 4+ anterior chamber cell/flare or 4+ vitritis)
- Adverse Events that, in the opinion of the investigator, may require medical intervention to prevent permanent loss of sight.

Any serious adverse event or sight-threatening event occurring in a subject from the time of study medication administration through the last follow up visit must be reported to the Sponsor within 24 hours, even if the SAE or sight-threatening event does not appear to be drug-related. In the event of an SAE or sight-threatening event, the following steps should be taken;

1. report the SAE or sight-threatening event to Dompé pharmacovigilance contact by fax or e-mail using the SAE form.
2. report the SAE or sight-threatening event to the relevant IRB according to local specific requirements.

Adverse Drug Reaction

An **Adverse Drug Reaction (ADR)** is defined as an adverse event for which there is a reasonable possibility that the drug caused the adverse event. For the purposes of IND safety reporting, "reasonable possibility" means there is evidence to suggest a causal relationship between the drug and the adverse event. Adverse events are to be considered unsuspected if the relationship to the study drug as described in the table in § 9.2.1 is none or unlikely; whereas any AE reported in the study having a possible, probable or highly probable relationship to study drug will be considered as an ADR.

Unexpected Adverse Event Or Unexpected Suspected Adverse Reaction

An adverse event or suspected adverse reaction is considered **unexpected** if it is not listed in the investigator brochure or is not listed at the specificity or severity that has been observed. For example, under this definition, hepatic necrosis would be unexpected (by virtue of greater severity) if the investigator brochure referred only to elevated hepatic enzymes or hepatitis. "Unexpected," as used in this definition, also refers to adverse events or suspected adverse reactions that are mentioned in the investigator brochure as occurring with a class of drugs or as anticipated from the pharmacological properties of the drug, but are not specifically mentioned as occurring with the particular drug under investigation. (CFR-Code of Federal Regulations Title 21 Sec. 312.32). The determination of expectedness should be made on the basis of the current IB [Reference: 4].

Suspected Unexpected Serious Adverse Reaction

A **Suspected Unexpected Serious Adverse Reaction (SUSAR)** is defined as an adverse reaction that is both unexpected (not consistent with the applicable product information) and also meets the definition of a Serious Adverse Reaction. SUSARs related to the IMP qualify for regulatory reporting.

